8.2.2. Electronic Diary

Maternal participants will be required to complete a reactogenicity e-diary through an application (see [Section 8.15](#)) installed on a provisioned device or on the maternal participant's own personal device. Maternal participants will be asked to monitor and record local reactions, systemic events, and antipyretic medication usage for 7 days following administration of the study intervention, where Day 1 is the day of vaccination. The reactogenicity e-diary allows recording of these assessments only within a fixed time window, thus providing the accurate representation of the participant's experience at that time. Data on local reactions, systemic events, and antipyretic medication usage reported in the reactogenicity e-diary will be transferred electronically to a third-party vendor, where they will be available for review by investigators and the Pfizer clinicians at all times via an internet-based portal.

Maternal participants originally randomized to placebo who subsequently receive BNT162b2 1 month following delivery, will not complete a reactogenicity e-diary but will have their local reactions and systemic events detected and reported as AEs in accordance with [Section 8.3.2](#).

If the maternal participant lives in an area with poor network connection (certain countries only), a study staff/field worker may visit the maternal participant in her home or contact her via phone daily after vaccination to assess and record local reactions, systemic events, and temperature each day (beginning in the morning) for 6 days following vaccination (Day 2 through Day 7) where this system of follow-up is well established. Maternal participants may call the site and report additional local reactions and systemic events at any time during the Day 1 through Day 7 reporting period. The study staff/field worker will be required to record these data on a provisioned device or an application on a personal device, thus providing the accurate representation of the maternal participant's experience at that time. For events persisting on Day 7 and use of antipyretic medication continuing on Day 7, the field worker will continue to visit the participant and record information until resolution.

At intervals agreed to by the vendor and Pfizer, these data will be transferred electronically into Pfizer's database for analysis and reporting. These data do not need to be reported by the investigator in the CRF as AEs.

Investigators (or designee) will be required to review the reactogenicity e-diary data online at frequent intervals as part of the ongoing safety review.

The investigator or designee must obtain stop dates from the participant for any ongoing local reactions, systemic events, or use of antipyretic medication on the last day that the reactogenicity e-diary was completed. The stop dates should be documented in the source documents and the information entered in the CRF.

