Protocol amendment 4	06 August 2021	
 • Added procedures in Section 8.14 to capture data pertaining to myocarditis and pericarditis in response to commitments made to CBER.

Document History		
Document	Version Date	Summary and Rationale for Changes
		
 • Added myocarditis and pericarditis in Sections 8.14 and 2.3.1 in response to commitments made to CBER. • Added a procedure to any visit that occurs sooner than 1 month after any vaccination in Sections 8.11 and 8.17 in response to commitments made to CBER. • Added myocarditis and pericarditis as AESIs in Section 8.3.8. • Added a statement on diversity in Section 5. • Added clarification to the infant SoA (Section 1.3.3) to collect the e-diary or assist the maternal participant to delete the application at Visit 3. • Administrative update in Section 8.11.1.7 to add collection of the e-diary or assist the participant to delete the application. • Corrected typographical errors throughout.
Protocol amendment 3	14 May 2021	
 • Reduced the study sample size based on regulatory feedback and evolving global availability of COVID-19 vaccines for pregnant women. • Modified the study objectives to align with the reduced sample size. • Removed the hypothesis-based efficacy objective, estimands, and endpoints. • Modified the statistical analysis timing to align with the reduced sample size and changes in the objectives.

Document History		
Document	Version Date	Summary and Rationale for Changes
		
 Updated a typographical error in the SoA regarding the need to collect AE information during the 1-week postdelivery follow-up call. Clarified that, if pregnancy outcome information was not obtained at the time of delivery, updated information should be provided at Visit 6. Added a modifier to inclusion criterion 8 regarding the need for a telephone as method of contact in Mozambique, so that the population is reachable based on location despite lack of routine access to telephones. Removed the collection of CD4 count and HIV viral load at Visit 101 in Sections 1.3.2 and 8.17.1 since this is duplicate information and will already be collected at Visit 7 in Section 1.3.1. Added “chills” to the definition of confirmed COVID-19 in maternal participants in Section 8.1.1.

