8.2. Safety Assessments

Planned time points for all safety assessments are provided in the [SoA](#). Unscheduled clinical laboratory measurements may be obtained at any time during the study to assess any perceived safety issues.

A clinical assessment, including medical history, will be performed on all maternal participants at the first visit to establish a baseline. Significant medical history and observations from any physical examination will be documented in the CRF.

AEs and SAEs are collected, recorded, and reported as defined in [Section 8.3](#).

Acute reactions within the first 30 minutes after vaccination will be assessed and documented in the AE CRF.

The safety parameters also include reactogenicity e-diary reports of local reactions and systemic events (including fever) and use of antipyretic medication that occur in the 7 days after administration of the study intervention, where Day 1 is the day of vaccination. Reactogenicity will not be collected in the e-diary for placebo recipients who subsequently receive BNT162b2 1 month following delivery. These prospectively self-reported occurrences of local reactions and systemic events are graded as described in [Section 8.2.2](#).

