8.3.2. Method of Detecting AEs and SAEs

The method of recording, evaluating, and assessing causality of AEs and SAEs and the procedures for completing and transmitting SAE reports are provided in [Appendix 2](#).

Care will be taken not to introduce bias when detecting AEs and/or SAEs. Open-ended and nonleading verbal questioning of the participant is the preferred method to inquire about AE occurrences.

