8.13. COVID-19 Surveillance (All Maternal Participants)

If a participant experiences any of the following from the time of vaccination (irrespective of perceived etiology or clinical significance), she is instructed to contact the site immediately and, if confirmed, participate in an in-person or telehealth visit as soon as possible, optimally within 3 days after symptom onset (and at the latest 4 days after symptom resolution).

Note that:

- If new symptoms are reported within 4 days after resolution of all previous symptoms, they will be considered as part of a single illness and a second illness visit is not required;
- Surveillance of potential COVID-19 symptoms should continue even if a participant has a positive SARS-CoV-2 test earlier in the study.

During the 7 days following each vaccination, potential COVID-19 symptoms that overlap with specific systemic events (ie, fever, chills, new or increased muscle pain, diarrhea, vomiting) should not trigger a potential COVID-19 illness visit unless, in the investigator's opinion, the clinical picture is more indicative of a possible COVID-19 illness than vaccine reactogenicity.

If, in the investigator's opinion, the symptoms are considered more likely to be vaccine reactogenicity, but a participant is required to demonstrate that they are SARS-CoV-2–negative, a local SARS-CoV-2 test may be performed: if positive, the symptoms should be recorded as a potential COVID-19 illness; if not, the symptoms should be recorded as AEs (unless already captured in the reactogenicity e-diary).

Maternal participants may utilize a COVID-19 illness e-diary through an application (see [Section 8.15](#)) installed on a provisioned device or on the participant's own personal device to prompt her to report any symptoms. Note that this does not substitute for a participant's routine medical care. Therefore, participants should be encouraged to seek care, if appropriate, from their usual provider.

- A diagnosis of COVID-19;
- Fever;
- New or increased cough;
- New or increased shortness of breath;
- Chills;
- New or increased muscle pain;
- New loss of taste/smell;
- Sore throat;
- Diarrhea;
- Vomiting.

8.13.1. Potential Maternal COVID-19 Illness Visit (Optimally Within 3 Days After Potential COVID-19 Illness Onset)

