3.5.2. E-Diary Transmission

For maternal participants, an e-diary will be considered transmitted if any data for the local reactions, systemic events, or use of antipyretic medication are present for any day. If all data are missing for all items on the e-diary for all 7 days after vaccination, then the e-diary will be considered not transmitted. E-diary data will not be collected from maternal participants originally assigned to placebo who subsequently receive BNT162b2 after delivery.

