6.4. Other Endpoints

The safety data and immunogenicity results for individuals with confirmed stable HIV disease will be summarized descriptively. Furthermore, VE may be assessed if there is a sufficient number of COVID-19 cases in this group of participants.

For maternal participants, the AEs, including SAEs, reported in the open-label follow-up period will be summarized separately from those reported during the blinded follow-up period.

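### Reactions that need only go in the e-diary during the blinded period are reported as AEs after crossover, so the open-label and blinded AE totals are on different definitions

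*Protocol*

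**What the plan says.** Protocol 8.2.2 sets two recording rules for the same kind of event.

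- **Blinded period.** Local reactions, systemic events and antipyretic use on Days 1 to 7 are entered in the e-diary, and "These data do not need to be reported by the investigator in the CRF as AEs". Protocol 8.13 works the same way for symptoms judged to be reactogenicity after a negative local test: "the symptoms should be recorded as AEs (unless already captured in the reactogenicity e-diary").
- **After crossover.** Placebo recipients who receive BNT162b2 after delivery "will not complete a reactogenicity e-diary but will have their local reactions and systemic events detected and reported as AEs". SAP 3.5.2 confirms the missing diary: "E-diary data will not be collected from maternal participants originally assigned to placebo who subsequently receive BNT162b2 after delivery".
- **Common to both periods.** "Acute reactions within the first 30 minutes after vaccination will be assessed and documented in the AE CRF" (Protocol 8.2). The visit procedures in Protocol 8.11 and 8.17 both apply this.

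For reporting, SAP 6.4 says that maternal AEs "reported in the open-label follow-up period will be summarized separately from those reported during the blinded follow-up period", and SAP 5.2.1 says the same. SAP 3.1.1.4 plans AE summaries by system organ class (SOC) and preferred term (PT). Neither document says that reaction terms in the open-label summary will be flagged, shown apart or footnoted.

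**The concern.** The open-label summary for the original placebo group describes the only planned two-dose BNT162b2 series given after delivery. A reader will naturally set it beside the blinded BNT162b2 AE table and read the difference as post partum against pregnancy. The two tables look alike: same vaccine, two doses, AEs to 1 month after the second. But an arm that is sore on Day 2 is a diary entry in one and an AE in the other. The any-AE and SOC percentages carry this difference with nothing to warn the reader. At stake is a recording artefact being taken for poorer tolerability after delivery.

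**Working it through.** The plan gives no figure for this effect, so there is none to reproduce. The check is a comparison of the rules, followed by an illustration of size.

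**1. Rules side by side**

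| | Blinded BNT162b2 | Placebo recipients after crossover |
|---|---|---|
| Day 1–7 reactions | E-diary; AE entry not required | No e-diary; reported as AEs |
| Reactions within 30 minutes | AE CRF | AE CRF |
| How AEs are found | Open questioning | Open questioning |
| Reaction terms in the AE total | Largely absent | Present when reported |

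Women originally given BNT162b2 do not enter this comparison. After Visit 4 they have SAEs collected, plus procedure-related AEs within 48 hours (Protocol 8.3.1).

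**2. Follow-up length.** The visit windows are 19–23 days between doses and 28–35 days after the second dose, in both schedules (Protocol 1.3.1 and 1.3.2). Each AE window is therefore 19 + 28 = 47 to 23 + 35 = 58 days. Length of follow-up neither causes nor cancels the difference.

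**3. Size.** Inputs:

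- r = 0.841, injection site reactions in C4591001 (Protocol 2.3). This is a solicited rate.
- c = share of those women whose reaction is captured as an AE. Not in the documents; assumed 10% to 50%. It should be below 100%, because "Open-ended and nonleading verbal questioning of the participant is the preferred method to inquire about AE occurrences" (Protocol 8.3.2), not a daily prompt.
- u = percentage with any AE other than these reactions. Not in the documents; assumed 10% to 30%, equal in both periods and independent of reactions.

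Open-label any-AE percentage = 1 − (1 − u)(1 − c·r). Excess over the blinded percentage u = (1 − u)·c·r.

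| u | c = 10% | c = 25% | c = 50% |
|---|---|---|---|
| 10% | +7.6 | +18.9 | +37.8 |
| 20% | +6.7 | +16.8 | +33.6 |
| 30% | +5.9 | +14.7 | +29.4 |

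Example: u = 20%, c = 25% gives 0.80 × 0.25 × 0.841 = 0.168, so 20% becomes 36.8%. Take 175 women per group, which is an upper bound for those who cross over. The Clopper-Pearson 95% intervals are then 14.3% to 26.7% for 35/175 and 29.4% to 44.2% for 64/175. They do not overlap, from recording alone.

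**4. What could cancel it.** The open-label figure equals the blinded one if the background rate falls to 1 − (1 − u)/(1 − c·r). At u = 20%, c = 10% this is 1 − 0.80/0.9159 = 12.7%, which is a plausible fall. At u = 20%, c = 25% it is 1 − 0.80/0.78975 = −1.3%, so no fall would be enough.

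**5. After the fix.** With reaction terms set aside, both totals estimate u and the excess in this model is 0.

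**The case against.** The strongest reply is that no planned analysis is biased. The primary AE estimand runs from Dose 1 through 1 month after Dose 2, both arms use the e-diary in that period, and no objective concerns vaccination after delivery or compares open-label with blinded AEs. The summaries are kept apart, and the recording rule is stated openly. SAP 3.1.1.4 gives each PT its own row, so injection site pain or fatigue can be recognized and other events remain visible. All of this stands, and it confines the point to how the any-AE and SOC totals will be read. Keeping the tables apart does not put those totals on one definition.

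Three stronger readings are tempting and are not supported:

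- **That the open-label percentage must come out higher.** The artefact acts upward, but background AE rates in late pregnancy and post partum may differ and neither is given. Step 4 shows that a fall could offset it at low capture.
- **That reactions are barred from the blinded AE record, or that other AEs are hidden in the open-label one.** The blinded text only removes the need to report, 30-minute reactions are AEs in both periods, and the PT rows remain.
- **That cardiac prompting adds a second upward shift.** Amendment 4 of 06 August 2021 "Added procedures in Section 8.14 to capture data pertaining to myocarditis and pericarditis", so a reader might infer that more open-label than blinded time was prompted. The documents give the end of enrolment but no first-enrolment date and no dates on which sites adopted the amendment, so the shares cannot be derived. Shortness of breath is in any case a blinded-period COVID-19 surveillance trigger under Protocol 8.13.

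**Conclusion.** The point holds as one of presentation. For the placebo recipients who cross over, the open-label any-AE and SOC percentages include Day 1–7 reactions that the blinded BNT162b2 percentages largely omit, over windows of the same length. The direction of the artefact follows from the protocol text. Its size does not: about +6 to +38 percentage points rests on the assumed capture of 10% to 50%, the assumed background of 10% to 30%, independence, and a reaction rate borrowed from C4591001. The randomized blinded comparison is untouched.

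**What to change.** In SAP 5.2.1 and 6.4, present the open-label AE totals for the original placebo group twice: with, and without, prompted-reaction terms with onset on Days 1 to 7 after Vaccination 3 or 4. The terms are injection site pain, redness and swelling; fever, fatigue, headache, chills, vomiting and diarrhea; and muscle or joint pain. Add a footnote that reactions were recorded differently in the two periods, and that only the total without these terms is broadly comparable with the blinded AE table. It is only broadly comparable because the blinded table keeps 30-minute reactions and any diary reaction that an investigator chose to enter as an AE.

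The cost is one flag derived from onset date and PT, and a few more rows. No new data are needed and study conduct does not change. The downside is slightly longer tables.

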8.2.2.4. Fever

In order to record information on fever, a thermometer will be given to maternal participants with instructions on how to measure oral temperature at home. Temperature will be collected in the reactogenicity e-diary in the evening daily during the reactogenicity e-diary reporting period. It will also be collected at any time during the reactogenicity e-diary data collection periods when fever is suspected. Similarly, based on local practice in certain countries/locales, the study staff/field worker will call or visit maternal participants daily during the reactogenicity reporting period to collect the temperature.

Fever is defined as an oral temperature of $\geq 38.0^{\circ}\text{C}$ (100.4°F). The highest temperature for each day will be recorded in the reactogenicity e-diary. Temperature will be measured and recorded to 1 decimal place. Temperatures recorded in degrees Fahrenheit will be programmatically converted to degrees Celsius and then categorized during analysis according to the scale shown in Table 4.

If a fever of $\geq 39.0^{\circ}\text{C}$ (102.1°F) is reported in the reactogenicity e-diary, a telephone contact should occur to ascertain further details and determine whether a site visit is clinically indicated. Only an investigator or medically qualified person is able to confirm a maternal participant's fever as $>40.0^{\circ}\text{C}$ ($>104.0^{\circ}\text{F}$). If a maternal participant experiences a confirmed fever $>40.0^{\circ}\text{C}$ ($>104.0^{\circ}\text{F}$), the investigator must immediately notify the sponsor and, if it is determined to be related to the administration of the study intervention, further vaccinations will be discontinued in that maternal participant.

Table 4. Scale for Fever

$\geq 38.0\text{-}38.4^{\circ}\text{C}$ ($100.4\text{-}101.1^{\circ}\text{F}$)
$>38.4\text{-}38.9^{\circ}\text{C}$ ($101.2\text{-}102.0^{\circ}\text{F}$)
$>38.9\text{-}40.0^{\circ}\text{C}$ ($102.1\text{-}104.0^{\circ}\text{F}$)
$>40.0^{\circ}\text{C}$ ($>104.0^{\circ}\text{F}$)

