- Perform an obstetric ultrasound scan and/or record findings to confirm singleton pregnancy and rule out fetal abnormalities.
- Record nonstudy vaccinations as described in [Section 6.5](#).
- Collect and record concomitant medication associated with AE/SAEs.
- Ensure and document that all of the inclusion criteria and none of the exclusion criteria are met.
- Ensure that the participant meets none of the temporary delay criteria as described in [Section 5.5](#).
- Explain the e-diary technologies available for this study (see [Section 8.15](#)) and assist the participant in downloading the study application onto her own device or issue a provisioned device if required.
- Record systemic events at baseline in the e-diary.
- Assign a single participant identifier using the IRT system.
- Collect a blood sample (approximately 20 mL) for immunogenicity testing.
- Obtain a nasal (midturbinate) swab (collected by site staff).
- Obtain the participant's randomization number and study intervention allocation using the IRT system.
- Unblinded site staff member(s) will dispense/administer 1 dose of study intervention into the deltoid muscle of the (preferably) nondominant arm. Please refer to the IP manual for further instruction on this process.
- Blinded site staff must observe the participant for at least 30 minutes after study intervention administration for any acute reactions. Record any acute reactions (including time of onset) in the participant's source documents and on the AE page of the CRF, and on an SAE form as applicable.
- Ask the participant to contact the site staff or investigator if the participant experiences acute chest pain, shortness of breath, or palpitations (see [Section 8.14](#)).

- Issue a measuring device to measure local reactions at the injection site and a thermometer for recording daily temperatures and provide instructions on their use. Provide instructions on e-diary completion and ask the participant to complete the reactogenicity e-diary from Day 1 through Day 7, with Day 1 being the day of vaccination, OR explain to the maternal participant that a study staff member/field worker will call or visit her every day from Day 2 through Day 7 after vaccination (where Day 1 is the day of vaccination) to collect or take her temperature and record systemic events, acute local reactions, and use of antipyretic medication in a diary (if applicable).

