3.1.1.1. Local Reactions

The local reactions assessed and reported in the e-diary are redness, swelling, and pain at the injection site, from Day 1 through Day 7 after each dose, where Day 1 is the day of each dose. Maternal participants originally randomized to placebo who subsequently receive BNT162b2 1 month following delivery will not complete a reactogenicity e-diary after receiving BNT162b2.

This section describes derivations with details for the assessment of local reactions: presence, severity level, duration, and onset day.

Presence or Absence

For each local reaction and any local reaction on any day, Table 3 explains the algorithm to derive the presence of a reaction (yes or no) during the interval from Day 1 through Day 7, where Day 1 is the day of each dose.

Table 3. Derived Variables for Presence of Each and Any Local Reaction Within 7 Days for Each Dose

Variable	Yes (1)	No (0)
Presence of each local reaction.	Participant reports the reaction as “yes” on any day (Day 1 through Day 7).	For each local reaction, participant reports the reaction as “no” on all 7 days (Day 1 through Day 7) or as a combination of “no” and missing on all 7 days (Day 1 through Day 7).
Presence of any local reaction.	Participant reports any local reaction as “yes” on any day (Day 1 through Day 7).	For all 3 local reactions, participant reports “no” on all 7 days (Day 1 through Day 7) or as a combination of “no” and missing on all 7 days (Day 1 through Day 7).

Note: Missing e-diary data will not be imputed. Participants with no e-diary data reported will not be included in the e-diary summaries.

Severity and Maximum Severity

Redness and swelling will be measured and recorded in measuring device units (range: 1 to 21) and then categorized during analysis as absent, mild, moderate, or severe based on the grading scale in Table 4. Measuring device units can be converted to centimeters according to the following formula: 1 measuring device unit = 0.5 cm. Pain at the injection site will be assessed by the participant as absent, mild, moderate, or severe according to the grading scale in Table 4.

Table 4. Local Reaction Grading Scale

	Mild (Grade 1)	Moderate (Grade 2)	Severe (Grade 3)	Potentially Life Threatening (Grade 4)
Pain at the injection site	Does not interfere with activity.	Interferes with activity.	Prevents daily activity.	Emergency room visit or hospitalization for severe pain.

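### Field-worker follow-up schedules no Day 1 contact, so a reaction confined to Day 1 and not called in is scored as absent in the primary Day 1–7 percentage

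*Protocol*

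**What the plan says.** SAP 3.1.1.1 assesses local reactions "from Day 1 through Day 7 after each dose, where Day 1 is the day of each dose". SAP 3.1.1.2 uses the same window and similar derivations for systemic events. Women on the e-diary route record all seven days.

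Protocol 8.2.2 describes a second route for certain countries with poor network connection. Staff or field workers visit or phone daily to "record local reactions, systemic events, and temperature each day (beginning in the morning) for 6 days following vaccination (Day 2 through Day 7". The Visit 1 procedures (Protocol 8.11.1) agree: "a study staff member/field worker will call or visit her every day from Day 2 through Day 7 after vaccination". Day 1 is not closed off. Protocol 8.2.2 adds that women "may call the site and report additional local reactions and systemic events at any time during the Day 1 through Day 7 reporting period", and staff must record what is reported.

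SAP Table 3 scores a reaction as present if it is reported on any one day. It is scored as absent if all seven days are 'no', or "as a combination of “no” and missing on all 7 days (Day 1 through Day 7". SAP 6.1.1.1.1 and 6.1.1.2.1 exclude a woman from the analysis of a dose only if she has no diary data at all for that dose.

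The protocol is not uniform on when field-worker contacts start. Section 8.2.2.4 has workers collect temperature daily over the reactogenicity reporting period, and 8.2.2.5 gives that period as Day 1 to Day 7. Sections 8.2.2 and 8.11.1 start at Day 2.

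**The concern.** Two collection schedules feed one primary percentage. On the e-diary route a missing Day 1 is an omission by the participant. On the field-worker route it is the expected state unless the woman calls. Table 3 treats both alike: a missing Day 1 followed by six 'no' entries becomes a non-reactor who stays in the denominator. The SAP says missing diary data are not imputed, but for a day left unscheduled by design the presence rule has the same effect as entering 'no'.

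At stake is a modest downward bias in the primary reactogenicity percentages, and a shift in the onset-day and duration summaries, for part of the study population. The plan has no summary by collection route that would show whether this happened.

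**Working it through.** **Day count.** The endpoint window, Day 1 to Day 7, is 7 days. Field-worker contacts, Day 2 to Day 7, are 6, matching the protocol's own figure. One day in seven (14%) has no scheduled assessment on this route.

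**What else covers Day 1.** The 30-minute observation after vaccination goes to the AE CRF (Protocol 8.2), not to the diary endpoint. Nothing tells the worker to ask about Day 1 at the Day 2 contact, and Protocol 8.2.2 says the e-diary accepts entries only within a fixed time window.

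**Table 3 applied to four field-worker patterns.**

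| Pattern | Day 1 | Days 2–7 | Scored |
|---|---|---|---|
| Day 1 only, not called in | missing | six 'no' | absent (wrong) |
| Day 1 only, called in | 'yes' | six 'no' | present |
| Starts Day 1, still there Day 2, not called in | missing | 'yes' on Day 2 | present |
| No data on any day | missing | missing | excluded |

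Only the first pattern is misclassified for presence.

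**Onset and duration.** SAP 3.1.1.1 defines onset as the first day reported and duration as last day − first day + 1. For a reaction on Days 1 to 3, the true onset is Day 1 and the duration is 3 − 1 + 1 = 3 days. Without a Day 1 report it becomes onset Day 2 and 3 − 2 + 1 = 2 days.

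**Size, by assumption.** Let p be the true reaction rate, f the share of women on the field-worker route, q the share of reactors whose reaction is confined to Day 1, and c the share of those who call in. Then:

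undercount in percentage points = 100 × p × f × q × (1 − c)

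The documents give none of f, q or c. For p, Protocol 2.2.1 reports rates in C4591001 (not pregnant women): injection site reactions 84.1%, fatigue 62.9%, fever 14.2%. The range below uses f from 0.10 to 0.50 and q from 0.10 to 0.30.

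| p | c = 0 | c = 0.5 | c = 1 |
|---|---|---|---|
| 84.1% | 0.84 to 12.6 | 0.42 to 6.3 | 0 |
| 62.9% | 0.63 to 9.4 | 0.31 to 4.7 | 0 |
| 14.2% | 0.14 to 2.1 | 0.07 to 1.1 | 0 |

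For example, 84.1 × 0.10 × 0.10 × 1 = 0.84, and 84.1 × 0.50 × 0.30 × 1 = 12.6. If f, q and c are equal in the two arms, both rates shrink by the factor 1 − fq(1 − c). The absolute loss is then larger in the arm with more reactions, and the between-arm difference shrinks by the same factor.

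**Why dropping the 'No' scores is not the remedy.** Take field-worker women only, with p = 62.9%, q = 0.10 and no calls. Table 3 gives 62.9 × 0.90 = 56.6%. If 'No' is not scored when Day 1 is missing, only the 56.6% with a later 'yes' remain in the denominator, and the rate is 56.6/56.6 = 100%. Keeping only women who have Day 1 data on this route selects those who called, who are again mainly reactors.

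**The case against.** The strongest reply is that the plan already covers most Day 1 events:

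- A reaction still present on Day 2 scores 'yes', and so does one called in.
- Protocol 8.11.1 and 8.11.1.1 tell women to contact the site at once, from Day 1, for fever of 39.0°C or more, redness or swelling over 10 cm, severe pain, or any severe systemic event. The most important Day 1 events do not rest on an optional call.
- Protocol 8.15 requires staff to contact women who are not completing the diary and to obtain missed events.
- The route is permitted only in certain countries and where such follow-up is established, so it may involve few women.
- Both arms use it, and every endpoint is descriptive (SAP 5.1).

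Most of this stands, and it limits the point to mild or moderate reactions that are over by the Day 2 contact. It does not remove the point. The general call is voluntary, on a route that exists because the network is poor, and 8.15 does not clearly reach a Day 1 that was never scheduled.

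A reader might go further in three ways that the documents do not support:

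- **All Day 1 reactions on this route are lost.** The second and third patterns in the table show otherwise.
- **Morning rounds miss evening fever.** "Temperature will be collected in the reactogenicity e-diary in the evening daily during the reactogenicity e-diary reporting period" describes the e-diary, and field-worker contacts begin in the morning. But women have their own thermometers, workers may collect a self-measured reading as well as take one (8.11.1), and the day's highest temperature is to be recorded (8.2.2.4).
- **The race and ethnicity subgroups in SAP 6.5 would reflect collection route.** Nothing in the documents links the two.

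Timing also matters. Enrollment ended on 25 October 2021 and the SAP is dated 31 March 2022. Allowing 28 days of screening and a 42-day dose interval, blinded dosing would have finished by about 3 January 2022. Women who cross over from placebo complete no reactogenicity diary. A change to collection probably comes too late.

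**Conclusion.** The point holds in a limited form. Followed as written, the plan scores as absent any field-worker reaction that is confined to Day 1 and not called in. It may also move the onset of longer Day 1 reactions to Day 2 and shorten their duration by a day. Reactions lasting into Day 2, and reactions called in, are counted correctly for presence.

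The direction is understatement. The amount cannot be computed from the documents. The 0.4 to 12.6 points for an 84.1% rate (none to half calling in) rests on assumed values of f, q and c and on a rate from nonpregnant participants. It is zero if every such woman calls, and very small if few women are on the route. With the same route in both arms, this is not a source of a false safety signal. It is a gap worth closing in the analysis, because these are primary safety percentages and the tables as planned could not reveal it.

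**What to change.** **SAP.** Keep the Table 3 rule for the main analysis. Add:

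1. A reactogenicity summary by collection route (e-diary or field worker), for each dose and vaccine group.
2. A sensitivity analysis of presence, onset day and duration restricted to women on the e-diary route, whose Day 1 was scheduled for collection. The arms stay comparable within this subset provided route is decided by where the woman lives and not by her reactions.

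Do not drop 'No' scores when Day 1 is missing, and do not restrict to women who happen to have Day 1 data. Both select for reactors.

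**Protocol.** Reconcile the Day 2 start in 8.2.2 and 8.11.1 with the daily collection over the Day 1 to Day 7 reporting period in 8.2.2.4 and 8.2.2.5, and state how Day 1 is captured on the field-worker route. Where collection is still open, have the existing Day 2 contact also record Day 1 reactions and the highest Day 1 temperature.

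**Cost.** A few extra tables and a route flag in the diary data. Any Day 1 entry made at the Day 2 contact would be next-day recall rather than real-time recording.
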